#### 5.0 Inclusion/Exclusion Criteria

- 5.1 Inclusion Criteria. Patients will be eligible for inclusion in the Pre-Randomization Phase of the MIND-USA study (i.e., consented for data collection but not yet randomized because disease- or drug-induced coma prevents assessment for delirium or because delirium is not present) if they are [1] adult patients (≥ 18 years old) [2] in a medical and/or surgical ICU and [3] on mechanical ventilation or non-invasive positive pressure ventilation (NIPPV), and/or being treated for shock (e.g., with vasopressors or intra-aortic balloon pump). Only patients who meet inclusion criteria, have no exclusion criteria (see section 5.2), and develop delirium (according to the CAM-ICU) will advance to the Interventional Trial Phase (i.e., the randomization phase) of the MIND-USA study (see section 6.2).
- **5.2 Exclusion Criteria**. Patients will be excluded (i.e., not consented) for any of the following reasons:
  - [1] Rapidly resolving organ failure criteria, indicated by *planned immediate* discontinuation of mechanical ventilation, NIPPV, and/or vasopressors at the time of screening for study enrollment, such that the patient will no longer meet inclusion criteria.
  - [2] Pregnancy or breastfeeding (negative pregnancy test required prior to randomization for female patients of childbearing potential)
  - Severe dementia or other chronic neurologic disease or disorder that either makes the [3] patient incapable of living independently at baseline or results in an IQCODE  $\geq 4.5$ (completed by the patient or their qualified surrogate). Examples include but are not limited to mental illness requiring long-term institutionalization, acquired or congenital mental retardation, Parkinson's disease, Huntington's disease, Alzheimer's disease, and debilitating cerebrovascular disease. Note: Subjects with mild to moderate dementia will be enrolled in the study. The rationale for inclusion of these typically elderly patients is that they represent an important, expanding group of older ICU patients who are very high risk for a protracted delirium course, and only very sparse data exist to direct treatment for this expanding group of elders. In light of the recent black box warning regarding longer-term use of antipsychotics in patients with dementia, this trial will be an ideal mechanism by which to expand knowledge of the safety profile for short-term use of these medications to treat delirium in patients with mild to moderate dementia. Acknowledging that delirium and dementia likely share some pathogenetic mechanisms,  subgroup analyses on these patients will help generate hypotheses for future aging research.
  - [4] Acute or subacute severe neurologic deficit that is expected to make the patient incapable of living independently after hospital discharge due to cognitive deficits. Examples include stroke, intracranial hemorrhage, cranial trauma, intracranial malignancy, anoxic brain injury, and cerebral edema.

MIND-USA Protocol Version: 1.15 Confidential Protocol Date: June 22, 2016 14 of 51

- [5] History of torsades de pointes, documented baseline QT prolongation (congenital long QT syndrome), or QTc ≥ 550 ms at screening due to refractory electrolyte abnormalities or other refractory/uncorrectable etiologies.
- [6] Ongoing maintenance therapy with typical or atypical antipsychotics or lithium^176, with plans by the ICU team to continue the medication during the current ICU stay.
- [7] History of neuroleptic malignant syndrome (NMS), haloperidol allergy, or ziprasidone allergy
- [8] Expected death within 24 hours of enrollment or lack of commitment to aggressive treatment by family or the medical team (e.g., likely withdrawal of life support measures within 24 hours of screening)
- [9] Inability to obtain informed consent from the patient or an authorized representative/surrogate for one of the following reasons:
  - (a) Attending physician refusal
  - (b) Patient and/or surrogate refusal
  - (c) Patient unable to consent and no surrogate available [Note: No longer using this exclusion]
  - (d) 72-hour period of eligibility was exceeded before the patient was screened
  - (e) Non-comatose patient unable to consent and no surrogate available within 72 hours of meeting all inclusion criteria
  - (f) Persistently comatose patient unable to consent and no surrogate available within 120 hours of meeting all inclusion criteria

When patients are unable to consent for themselves on enrollment, a consent/reconsent process will be used (surrogate consent at enrollment and re-consenting patients when competent), in keeping with recent literature on consenting delirious and/or ICU patients. 177,178

- [10] Blindness, deafness, or inability to speak or understand English, the latter only if at a center without Spanish-speaking research staff, since Spanish-speaking patients are eligible at sites that have Spanish-speaking research staff, these patients will not be followed in the long-term follow-up phase of the trial (see section 7.4) since the testing materials are primarily available only in English.
- [11] Incarceration, since prisoners may be difficult to test during long-term follow-up
- [12] Current enrollment in a study that does not allow co-enrollment or an interventional trial that uses delirium as a primary outcome

**Special Note about Patients with a history of seizures**. Subjects with a *history of seizures* on and off antiepileptics who meet inclusion criteria and no exclusion criteria will be eligible for enrollment into the MIND-USA study. These antipsychotics pose minimal risk of lowering the seizure threshold. The presence of a seizure disorder in patients with schizophrenia or bipolar disorder is not a contraindication for use of haloperidol, ziprasidone, or other antipsychotics. Patients with a history, who are currently on therapy specifically for this indication, will be continued on antiepileptic medications and have the drug levels monitored by the medical team as indicated within usual practice.

MIND-USA Protocol Version: 1.15 Confidential Protocol Date: June 22, 2016 15 of 51

#### 6.0 Enrollment/Randomization

- **6.1.** Screening and Obtaining Informed Consent (Pre-Randomization Phase). Study personnel at each site will screen every day using the ICU census. When an eligible patient is identified (i.e., inclusion criteria are met and no exclusion criteria are present), informed consent will be pursued; when obtained, the patient will be included in the Pre-Randomization Phase of the study, which will include approximately 1,300 participants. Surrogate consent will be required for most patients because during the initial phase of their illness they will often be either comatose or delirious. However, all patients consented via surrogate will be re-consented for participation in the trial once competent. 177,178
- **6.2. Randomization (Interventional Trial Phase)**. Once informed consent is obtained, patients will be assessed twice daily for delirium using the CAM-ICU. When a patient becomes delirious (i.e., CAM-ICU positive), they will advance to the Interventional Trial Phase of the study and be assigned via randomization to one of the three treatment groups. Based on the most recent screening data from participating sites, we estimate 50%-60% of approximately 1,100 patients included in the pre-randomization phase will develop delirium, often after a short period of coma. We will thus be able to randomize 561 or more patients to participate in the Interventional Trial Phase, meeting our calculated sample size (see Section 11.1).

Randomization will be conducted in a 1:1:1 ratio to treatment with haloperidol, ziprasidone, or placebo using a computer-generated randomization scheme (with permuted block sizes of 6 and 8) stratified by study center and age (< 70 years vs.  $\ge 70$  years). The randomization scheme will be created by the study's primary biostatistician and will be distributed directly to the investigational pharmacy at each study site as a set of randomization lists stratified by study center and age (< 70 years vs.  $\ge 70$  years). Once a consented patient has become delirious and an order for blinded study drug is placed, the investigational pharmacist will refer to the appropriate randomization list (determined by the patient's age) to establish that patient's treatment assignment. The lists will only be accessible to investigational pharmacists, so that treatment assignment will be known only by the investigational pharmacists.

**6.3 Blinding**. Apart from the investigational pharmacists, all study personnel, patients, and clinicians will remain blinded to each patient's treatment assignment throughout enrollment, follow-up, and data analysis. If an AE is considered study-drug related, unexpected and serious, the study drug will be immediately discontinued and the event will be reviewed via the usual process, which may involve unblinded evaluation by the Clinical Monitor, as outlined in the Data Safety Monitoring Plan (see sections 9.2 & 9.3).

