- Initiation. A pre-randomization 12-lead ECG will be obtained prior to study drug initiation to assess QTc. If this ECG shows QTc  $\geq$  550 ms, randomization and study drug initiation will be delayed until reversible causes for the QTc prolongation are found and treated. When the QTc becomes < 550 ms, randomization may occur and study drug may be started. For those patients whose ECG shows QTc < 550 ms, the first dose of study drug will be administered immediately after delirium diagnosis and randomization at a dose of 2.5 mg haloperidol IV (or 1.25 mg for patients  $\geq$  70yrs old), 5 mg ziprasidone IV (or 2.5 mg for patients  $\geq$  70yrs old), or 0.5 mL placebo (or 0.25 mL for patients  $\geq$  70yrs old).
- [4] **Titration**. After study drug initiation, subsequent study drug doses will be titrated twice daily—with all doses being delivered at approximately 10AM or 10PM—by doubling (increasing by 100%) or halving (decreasing by 50%) the volume according to the following rules. \*Note: An exception to this schedule will occur if the initiation dose is given after 4PM, in which case the second study drug dose will be given approximately 6 hours after the initiation dose (rather than at 10PM).
  - (a) Titrating Up. If study drug is not at maximum dose, the volume will be doubled approximately every 12 hours until the maximum dose is reached (10 mg haloperidol/20 mg ziprasidone/2 mL placebo q12h) unless [1] the patient cannot be assessed with the CAM-ICU due to coma (see section 7.3.1.[4].(b) below) or [2] study drug has been restarted after being held for safety reasons (see section 7.3.1.[5] on Holding study drug). If study drug has been held and then restarted (see section 7.3.1.[5] on when study drug can be restarted after Holding), the volume will not be titrated up but will instead be maintained at half the dose that had been held as long as side effects do not recur.
  - (b) Maintaining Current Dose. If a patient cannot be assessed with the CAM-ICU due to coma that is drug-induced (i.e., RASS -4 or -5 while receiving sedatives), study drug will be maintained at the current volume. Note: Sedative-induced coma is not considered a safety reason to hold study drug, whereas study drug will be held if sedatives have been held > 12 hours and the patient is comatose (per section 7.3.1.[5].(c) below).

MIND-USA Protocol Version: 1.15 Confidential Protocol Date: June 22, 2016 20 of 51

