- (c) Titrating Down. If a patient is determined to be CAM-ICU negative (i.e., not delirious) on two consecutive assessments, the study drug volume will be halved approximately every 12 hours to a minimum volume of 0.25 mL. When a patient has been CAM-ICU negative for 4 consecutive study CAM-ICU assessments, study drug will be discontinued regardless of the dose.
- (d) Restarting Study Drug. If at any time during the Treatment Period a patient is noted to develop a new episode of delirium **and** is in the ICU setting, study drug will be restarted at the dose most recently administered, as long as study drug was not discontinued permanently for safety reasons (see **Permanent Discontinuation** section below). If study drug is restarted after being temporarily held for safety reasons (as described in section 7.3.1[5]), it will be restarted at half the dose that was being administered when the safety concern was noted and prompted the study drug to be held.
- [5] **Holding**. Throughout the trial, study drug will be temporarily held for the following safety reasons:
  - (a) QTc Prolongation (≥ 550 ms). If a pre-dose 12-lead ECG (obtained per sections 7.3.1.[5].(a).(i) or (iii) below) confirms QTc ≥ 550 ms, study drug will be held. If a reversible cause for the QTc prolongation is found and treated and QTc becomes < 550 ms, study drug may be resumed at half the previous dose (not less than the minimum volume of 0.25 mL) as in our MIND pilot study and other recent studies. During the Interventional Trial Phase, QTc will be measured as follows:
    - (i) A pre-randomization 12-lead ECG will be obtained prior to study drug initiation.
    - (ii) Subsequently, QTc will be checked and documented prior to the administration of each dose of study drug, either manually calculated from a bedside telemetry strip using the Bazett formula (QTc = QT /  $\sqrt{RR}$  interval) or via software algorithms available in some bedside telemetry machines. Whenever these pre-dose measurements show a QTc  $\geq$  550 ms, a 12-lead ECG will be obtained to confirm that QTc  $\geq$  550 ms.

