  - (b) Extrapyramidal symptoms (EPS). If the patient develops clinical EPS, including dystonia and/or symptoms detected by the modified Simpson-Angus Scale(see section 7.3.2.[2]), then the study drug will be held and the patient treated as clinically indicated by the ICU team, who will be notified of the EPS by study staff. Upon resolution of EPS, study drug will be resumed at half the previous dose (not less than the minimum of 0.25mL).
  - (c) Oversedation. If the patient is oversedated (i.e., > 1 RASS level deeper than ICU team's sedation target), two sequential steps will be taken: [1] **sedatives** (including analgesics being used for sedation) will be held or decreased for > 12 hours per the ICU team's standard protocol and study drug will be maintained at current dose or titrated per standard titration rules (see section 7.3.1.[4]), then [2] **study drug** will be held if sedatives have been held > 12 hours and the patient remains oversedated. In this case, study drug will be restarted at half the previous dose (not less than the minimum of 0.25 mL) when oversedation resolves (i.e., RASS is within 1 of the ICU team's target).

MIND-USA Protocol Version: 1.15 Confidential Protocol Date: June 22, 2016 21 of 51

- [6] **Permanent Discontinuation**. Study drug will be permanently discontinued at any time during the trial for any of the following safety reasons:
  - (a) Neuroleptic malignant syndrome (NMS)
  - (b) Torsades de pointes or another ventricular tachycardia (VT) that results in clinical sequelae (e.g., hypotension) and/or requires treatment
  - (c) New-onset coma due to a known structural brain disease such as stroke, intracranial hemorrhage, cranial trauma, malignancy, anoxic brain injury, or cerebral edema
  - (d) Drug reaction with eosinophilia and systemic symptoms (DRESS) syndrome
  - (e) Any other study drug-related, life-threatening, serious adverse event

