- **7.3.2 Monitoring**. The risks of haloperidol and ziprasidone include tardive dyskinesia, neuroleptic malignant syndrome (NMS), extrapyramidal side effects (EPS), torsades de pointes and other arrhythmias, and hyperglycemia. Throughout the Treatment Period, study personnel will carefully monitor all patients daily for evidence of these potential adverse effects, determine study drug efficacy and safety, and monitor other factors that may influence outcomes. The above section describes how study drug will be titrated, held, or permanently discontinued should adverse effects occur. Additionally, all patients will be monitored carefully throughout the Post-Study Drug Period, which includes the four full calendar days after study drug is discontinued. Note: For patients who receive no study drug after day 10 post-randomization, daily monitoring will conclude at the end of the Treatment Period (i.e., at hospital discharge, death, or day 14 post-randomization, whichever occurs first) because the Post-Study Drug Period for these patients will be contained within the Treatment Period. Alternatively, patients who continue to receive study drug after day 10 post-randomization will be monitored through the end of the Post-Study Drug Period, which will extend beyond the Treatment Period.

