#### 8.0 Risks

- 8.1 Side Effects of Study Drug (Haloperidol and Ziprasidone). The risks of antipsychotics (haloperidol and ziprasidone) include tardive dyskinesia, neuroleptic malignant syndrome, extrapyramidal side effects (EPS), torsades de pointes and other arrhythmias, and hyperglycemia. Throughout the Interventional Trial Phase, study personnel will carefully monitor all patients for evidence of these potential adverse effects of the study drugs. These assessments are described above in section 7.3.2. Adverse events will be monitored closely and reported as described below in Section 9.0. Should any of these occur, adverse events will be reported to the coordinating center, with Serious Adverse Events reported within 24 hours. In addition, study drug will be titrated, held, or permanently discontinued, depending on the adverse effect, according to study protocol (see section 7.3.1). Both haloperidol and ziprasidone are pregnancy category C medications, and female patients of childbearing age must have a negative pregnancy test to meet entry criteria.
- **8.2 Risks from Blood Draws.** All patients will have blood drawn for research purposes. Having blood drawn is commonly painful, and it can rarely lead to bleeding, bruising, or infection at the site of the blood draw. For this reason, it will be our standard approach whenever possible to obtain blood for research purposes through existing intravenous peripheral, central or arterial catheters since patients routinely have such catheters while in the ICU. The volume of blood collected for research specimens represents a small percentage of the amount of blood taken during the course of a standard ICU stay and will not represent a significant risk to the patient.
- **8.3 Steps Taken to Reduce Risks and Increase Impact of Study**. We have taken the following steps in designing our protocol to minimize risk for the study population and to maximize the ultimate impact of this investigation on the field of medicine.
  - [1] All interventions included in the MIND-USA study are supported by a well-grounded and clearly described rationale suggesting potential, though unproven, benefit for eligible patients.

MIND-USA Protocol Version: 1.15 Confidential Protocol Date: June 22, 2016 28 of 51

- [2] All interventions are common and with established equipoise within the context of usual care and considered good or competent care in light of an absence of clear proof in favor of one over the other.

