 - Whether study treatment was ever held or permanently discontinued, and reasons for hold/discontinuation
- Dose level:
 - Proportion of opportunities to receive study treatment which were given, temporarily held, or permanently discontinued
 - Amount (mL) of each dose given
 - Whether dose amount was maintained, increased, or decreased
 - Reasons for hold or discontinuation

Definition and description of protocol noncompliance

Any noncompliance that increased safety risk to the patient was considered protocol noncompliance. These events will be captured for a variety of causes considered related to patient safety and will be described in the final study report, broken down according to a simple categorization scheme followed prospectively during the conduct of the MIND-USA investigation.

Analysis Populations

All analysis will be conducted on the randomized, intent-to-treat population. We will also compare demographic and admission characteristics of patients who were enrolled but not randomized to those who were randomized.

Analysis for all **in-hospital** outcomes will include all randomized patients in an intent-to-treat manner, with the following exceptions:

- Liberation from mechanical ventilation will include only patients who were on mechanical ventilation (invasive or noninvasive) at or within 24 hours following the time of randomization.
- 2. ICU readmission will include only patients who survived and remained in the study with access to medical data throughout their first ICU admission.

Analysis for **long-term** outcomes will include all patients who survive and remain in the study at the specified time point (3 or 12 months after randomization), and who have data for the outcome in question. We will describe the general cohort of patients who are included in any long-term outcome models at each time point.

5. Trial Population

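### Section 6.3 stops study drug after any SUSAR, but the permanent-discontinuation list in 7.3.1[6] leaves out SUSARs that are neither named nor life-threatening, so the restart rule does not clearly bar them

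*Protocol*

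**What the plan says.** **The stop.** Protocol 6.3 (Blinding) states: "If an AE is considered study-drug related, unexpected and serious, the study drug will be immediately discontinued". It sends the event on for review under 9.2 and 9.3. It does not say whether the stop is permanent and gives no restart condition.

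**Permanent stops.** Protocol 7.3.1[6] lists NMS; torsades, or other VT with clinical consequences or needing treatment; new coma from known structural brain disease; DRESS; and a catch-all: "Any other study drug-related, life-threatening, serious adverse event".

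**Restart.** Under 7.3.1[4](d), when a patient in the ICU has a new delirium episode during the Treatment Period, "study drug will be restarted at the dose most recently administered, as long as study drug was not discontinued permanently for safety reasons". A pointer to the Permanent Discontinuation item follows.

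**Holds.** 7.3.1[5] lists three temporary safety holds: QTc of 550 ms or more, EPS, and oversedation. After one of these, [4](d) restarts at half dose, and under [4](a) "the volume will not be titrated up but will instead be maintained at half the dose that had been held".

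**Seriousness and review.** Section 9.2.2 makes an event serious on several grounds besides threat to life, among them a prolonged hospital stay and significant incapacitation. Section 9.3[2] has the DSMB Chair review each SUSAR. It explains that sites need no unblinding because drug will already have been stopped under the titration rules.

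**The concern.** Sites dose from 7.3.1, and that section has no stop rule for SUSARs in general. The only one is in the blinding section, and it does not say how long the stop lasts. The restart rule is directive and has a single exception, which refers the reader to a list that most non-life-threatening SUSARs would not be on.

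At stake is patient safety in a rare case. On a literal reading, a suspected serious and unexpected reaction gets weaker protection against re-exposure than a QTc, EPS or oversedation hold. Section 9.3[2] sets no deadline for the outcome of the Chair's review, and no rule tells a blinded site to withhold drug until that outcome is known.

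**Working it through.** The plan states no figure on this point, so there is nothing to reproduce. The check follows one event through the rules and then does the dose arithmetic that the literal reading implies.

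**Rule trace.** Take an event that is drug-related, unexpected and serious because it prolongs the hospital stay. It is not life-threatening and not named in 7.3.1.

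| Step | Rule | Result |
|---|---|---|
| 1 | 6.3 | Drug stopped; duration not stated |
| 2 | 7.3.1[6], named items | Not met |
| 3 | 7.3.1[6], catch-all | Not met, because not life-threatening |
| 4 | 7.3.1[5] holds | Not met, so neither the half-dose restart nor the bar on up-titration applies |
| 5 | 7.3.1[4](d), new ICU delirium in the Treatment Period | Restart at the last dose, unless the 6.3 stop counts as permanent |

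The result turns on step 5. The word *discontinued* does not settle it. In 7.3.1[4](c) drug is *discontinued* after four consecutive negative CAM-ICU assessments, and [4](d), the next item, reverses that stop. Where permanence is meant, 7.3.1[6] says so.

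**Dose bound under the literal reading.** Inputs from 7.3.1: haloperidol 5 mg/mL, ziprasidone 10 mg/mL, minimum 0.25 mL, maximum 2 mL, doubling about every 12 h. Doses are haloperidol/ziprasidone in mg.

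- Restart under [4](d) = last volume.
- Restart after a hold = the larger of half the last volume and 0.25 mL, and that is also the later ceiling.
- Ceiling after a [4](d) restart = 2 mL.

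| Last dose | Restart, [4](d) | Restart after a hold | Restart ratio | Doublings to 2 mL | Ceiling ratio |
|---|---|---|---|---|---|
| 0.25 mL | 1.25/2.5 | 1.25/2.5 | 1 | 3 (36 h) | 2/0.25 = 8 |
| 0.5 mL | 2.5/5 | 1.25/2.5 | 2 | 2 (24 h) | 2/0.25 = 8 |
| 1 mL | 5/10 | 2.5/5 | 2 | 1 (12 h) | 2/0.5 = 4 |
| 2 mL | 10/20 | 5/10 | 2 | 0 (0 h) | 2/1 = 2 |

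The doublings assume that the patient stays delirious without coma or a new hold. The larger ratios need a low last dose. Starting from 0.5 mL, standard titration reaches 2 mL after two doublings, about 24 h. From the 0.25 mL start used at age 70 or over it takes three, about 36 h. At 2 mL both ratios are 2. In the placebo group the difference in antipsychotic dose is zero.

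**How many patients.** This cannot be computed. No SUSAR rate is given, and 9.1 keeps 13 categories of clinical outcome out of AE reporting by default. Delirium must also resolve and recur in the ICU by day 14; a patient who simply remains delirious does not meet [4](d).

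**The case against.** The strongest reply is that the 6.3 stop is meant to be permanent and that [4](d) already respects it, because its pointer to 7.3.1[6] does not claim that the list is exhaustive. The surrounding text supports this:

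- Reversible safety stops are called holds throughout 7.3.1[5]; 6.3 does not use that word.
- Section 7.3.2 recognises only three responses: "The above section describes how study drug will be titrated, held, or permanently discontinued should adverse effects occur". Section 8.1 repeats them: "study drug will be titrated, held, or permanently discontinued, depending on the adverse effect".
- The SAP (section 4, presentation of adherence) plans to report: "Proportion of opportunities to receive study treatment which were given, temporarily held, or permanently discontinued". It has no category for a reversible safety discontinuation.
- The reason given in 9.3[2] for keeping sites blinded makes most sense if the stop lasts.
- The reversible use in [4](c) concerns resolved delirium, not safety.

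There are also practical barriers. The site must tell the coordinating center within 24 h of the event, and the center must tell the DSMB Chair within a further 24 h, so the Chair should know within 24 + 24 = 48 h. Drug is prepared only on orders from study personnel, and section 10 allows withdrawal by the investigator or at the attending physician's request.

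Most of this stands. Permanence is the likelier intent, and an actual restart is unlikely. But the text that supports permanence describes or reports; it does not direct dosing. Notification and discretionary withdrawal are not a rule against restart. CAM-ICU is done twice daily in the ICU and a new episode is not defined, so a restart before the Chair has been told cannot be ruled out.

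**Conclusion.** Sections 6.3 and 7.3.1 do not agree on what follows a SUSAR stop. For an event that is neither named nor life-threatening, the dosing section read literally allows restart at the full last dose. This is a drafting gap of minor severity. It touches a small, uncountable set of patients and leaves ITT analysis, alpha and power unchanged.

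A reader might infer three stronger things, none of which the documents support:

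- *That the plan intends re-exposure at full dose after a SUSAR.* The wording in 7.3.2, 8.1, 9.3[2] and the SAP points the other way.
- *That a 2- to 8-fold higher dose is to be expected.* Those ceilings bound one literal reading of a rare sequence. They are not expected exposures.
- *That 6.3 directly contradicts the EPS resume rule in 7.3.1[5](b).* The two collide only if the EPS is drug-related, worse than the critical illness would explain (9.1), unexpected against an investigator's brochure that is not among the documents (9.2.3), serious, and not life-threatening.

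The conclusion assumes that sites apply 7.3.1 as written and that no site instruction outside these documents already bars restart.

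**What to change.** 1. Add an item to 7.3.1[6]: any SUSAR, that is, any event judged drug-related, unexpected and serious (see 6.3). The exception in [4](d) then applies without further change.
2. Insert *permanently* in the stop sentence of 6.3.
3. State that this takes precedence over the resume rules in 7.3.1[5], so that a hold event that also qualifies as a SUSAR is not resumed.
4. In 9.3[2], cite 7.3.1[6] in place of the titration rules, which contain no such stop.

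Restart after clearance by the DSMB Chair is not a good alternative. The Chair may see unblinded data, so a clearance sent to a blinded site could signal placebo. It would also give the Chair a patient-level role in dosing that 9.3[2] does not provide.

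The cost is one list item, one word and two cross-references, plus a note to sites. Because 9.2.1 asks only for a reasonable possibility of relatedness, a few patients will lose further study drug for events later judged unrelated. They remain in the ITT analysis.
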